6.8 Subject Diary

A diary will be handed out to the subject at Visit 1, Visit 2, and Visit 3.

- Every time gel is applied, the subject must document the time and date of application. This includes gel applied at the clinic site
- Pain intensity and pain relief will both be assessed by the subjects every 2 hours ± 30 minutes (after starting study drug) until the subject goes to bed on the evening of Day 1. The same assessment and recording frequency will also be followed starting with the first dose on Day 5. On Day 1 and Day 5 where an assessment time point coincides with a dosing time point, the assessment of pain intensity and pain relief should be made prior to the dose. For all other time periods, pain intensity and pain relief will be assessed and recorded immediately prior to each study drug application.
- Every time rescue medication is taken (not allowed within 6 hours of Study Visits and within 12 hours of Study Visit 3), the subject must document:
 - Time and date of rescue medication
 - Number of tablets taken
 - Reason for use of rescue medication
 - $\circ\,$ Pain intensity and pain relief immediately prior to each dose of rescue medication

The Investigator or designee will ensure that all diary entries completed by the subject are legible. The Investigator will review the diary at each clinic visit. The diary handed out to subjects on Visit 1, Visit 2, and Visit 3 will be collected by the Investigator or designee at Visit 2, Visit 3, and Visit 4 (Day 8±1) respectively.

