6.10 Rescue Medication

The investigator will provide rescue medication (paracetamol, 500 mg tablets) to the subject at the baseline visit. Rescue medication will be re-dispensed on Day 5 (V3), if necessary.

Subjects will be instructed to take only the rescue medication provided for pain in the ankle or any other pain (e.g., headache) or fever (e.g., due to common cold) they might experience during the trial. One tablet may be taken, repeated after at least 4 hours, if needed, up to a maximum of 2000 mg (four tablets) per day. No rescue medication is allowed within 6 hours prior to the study visits or within 12 hours of Study Visit 3.

The subject will receive a Subject Diary at Visit 1, Visit 2, and Visit 3 to record the information described in Section 6.8. At each visit, the investigator or designee will review the rescue medication use recorded in the diary and will transfer the relevant information to the CRF. Empty packages and rescue medication not used will be returned to the investigator. The investigator or designee will then compare the packages vs. the subject's rescue medication form and any discrepancies will be noted in the CRF.

The investigator will further investigate any instances in which rescue medication was taken for reasons other than ankle sprain and complete the Adverse Event Form, if appropriate.

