7.2 Lost to Follow up

A subject will be considered lost to follow up if he or she repeatedly fails to return for scheduled visits and is unable to be contacted by the study site.

If a subject fails to return to the site for a required study visit the site must attempt to contact the subject and reschedule the missed visit as soon as possible and counsel the subject on the

> GlaxoSmithKline Consumer Healthcare Confidential Template Version Effective: 18-May-18 (CCR #11475) Page **33** of **64**

importance of maintaining the assigned visit schedule and ascertain whether or not the subject wishes to and/or should continue in the study.

Before a subject is deemed lost to follow up, the investigator or designee must make every effort to regain contact with the subject (where possible, 3 telephone calls and, if necessary, a certified letter to the subject's last known mailing address or local equivalent methods). These contact attempts should be documented. If contact is made with the subject, the investigator should inquire about the reason for withdrawal, request that the subject return all products that they had been dispensed and if appropriate request that the subject return for a final visit, and follow-up with the subject regarding any unresolved adverse events (AEs).

Final safety assessments may be carried out when the subject returns to the study site, at the investigator's discretion, which could include the following:

- Physical examination and vital signs;
- Blood and urine specimens for safety laboratory and pregnancy tests (if applicable)

Should the subject continue to be unreachable, he/she will be considered to have withdrawn from the study and lost to follow up.

Lack of completion of all or any of the early termination procedures will not be viewed as protocol deviations so long as the subject's safety was preserved.

If the subject withdraws from the study and also withdraws consent for disclosure of future information, no further evaluations should be performed and no additional data should be collected. The sponsor may retain and continue to use any data collected before such withdrawal of consent.

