- POM, tenderness, ankle swelling, and ankle joint function (total score and subcategories) will be assessed
- Count and document remaining rescue medication.
- If insufficient rescued medication remains, additional rescue medication may be dispensed
- No rescue medication is allowed within 12 hours of this Visit
- Collect Visit 2 subject diary
- Dispense Visit 3 subject diary and instruct subject about appropriate use

8.2.3 Visit 4 /Day 8 ± 1

Procedures for this visit are also to be completed if the subject terminated the study prematurely.

- Changes in concomitant medication or non-drug treatments/procedures will be documented in the CRF.
- Spontaneous reporting of adverse events and those elicited by asking subjects to respond to a non-leading question such as "How do you feel?" will be assessed and any AEs recorded in the CRF.
- Subject continued eligibility
- The 4 tubes of study medication will be weighed. The weight of each tube will be documented in the CRF
- Collect remaining study medication and rescue medication
- Review diary
 - Review time and date of each gel application
 - Review scores for Pain Intensity and Pain Relief
 - \circ Review rescued medication use.
- Collect Visit 3 subject diary
- Perform a general physical examination including vital signs

GlaxoSmithKline Consumer Healthcare Confidential Template Version Effective: 18-May-18 (CCR #11475) Page **37** of **64**

Diclofenac Diethylamine 2.32% Study 211206 Protocol Amendment 1

- Urine pregnancy test (women of child bearing potential only)
- Safety laboratory blood samples for chemistry and hematology. Any subject with a clinically significant abnormality will be followed until its resolution.
- POM, tenderness, ankle swelling, and ankle joint function (total score and subcategories) will be assessed
- Count and document remaining rescue medication

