8.4 Follow-up Visit / "Phone Call"

The study site may contact a subject to follow up an AE post-study completion/withdrawal and, in some circumstances, request they return to the site for additional follow-up visits (final safety assessments). If needed, additional examinations may be carried out at such visits.

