#### 4.4.3 Rescue Medication

The investigator will provide rescue medication (paracetamol 500mg tablets) to the subjects at the baseline visit. Rescue medication will be re-dispensed on Day 5 i.e.at Visit 3. Subjects are not allowed to take rescue medication within 6 hours of study visits and within 12hours of Day 5. Following information will be documented in the Rescue Medication CRF page –

- Rescue medication taken (yes/no) (RMYN)
- Pain intensity (RMPI) and pain relief (RMPR) before taking rescue medication
- Reason for use of rescue medication (RMREAS)
- Time (RMSTTM) and date (RMSTDTC) of rescue medication
- Number of tablets taken (RMNUM)

Summuary of all the above mentioned points will be displayed in PPD . and will be listed in PPD .

Time to first use of rescue medication will be analyzed using the survival estimate of median time to event for each treatment group along with the CI for median. P-value from Log Rank test will be used to compare the median times between the treatment groups (**PPD**).

Kaplan Meier plot will be presented for the survival probabilities against the time points for both the treatment groups (In case number of events are considerable).

Subjects with no use of rescue medication will be censored at their last available date in the study.

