#### **Censoring Rule:**

GlaxoSmithKline Consumer Healthcare Confidential

Page 18 of 36

Event : If event occurred then value of censor is 0, time will be derived as follows: Date of First Occurrence of Event- Date of Randomization + 1

Censor: If event not occurred then value of censor is 1, time will be derived as follows: Last Available Date in the study - Date of Randomization + 1

Where, Last Available Date in the study = Maximum of (Date of Discontinuation, Date of Death, Date of Follow-up, Study Completion Date)

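### Time to first rescue use is censored at the latest administrative date and not at the end of diary coverage, so some lost or withdrawn subjects count as rescue-free on days nobody observed

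*SAP*

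**What the plan says.** SAP 4.4.3 analyses time to first rescue use by Kaplan-Meier median and log-rank test: "P-value from Log Rank test will be used to compare the median times between the treatment groups". Its rule for everyone else is: "Subjects with no use of rescue medication will be censored at their last available date in the study". The Censoring Rule that follows defines that date: "Where, Last Available Date in the study = Maximum of (Date of Discontinuation, Date of Death, Date of Follow-up, Study Completion Date". The SAP does not say what the follow-up date is and has no rule for a diary that is not returned. SAP 4.5.3 declines to impute missing diary scores, but only for pain intensity and pain relief.

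The protocol shows where rescue data come from. Under section 6.10 the investigator is to "review the rescue medication use recorded in the diary and will transfer the relevant information to the CRF" at each visit. Section 6.8 fixes when the diaries come back: "The diary handed out to subjects on Visit 1, Visit 2, and Visit 3 will be collected by the Investigator or designee" at Visits 2, 3 and 4 respectively. For early leavers, section 8.2.3 adds: "Procedures for this visit are also to be completed if the subject terminated the study prematurely". Those procedures include return of the diary and of the rescue tablets.

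SAP section 5 states that the protocol's Hodges-Lehmann analysis of rescue use has been replaced by the time-to-event analysis.

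**The concern.** A subject should stay in the risk set only while an event could be seen. None of the four dates in the SAP definition is tied to rescue observation, and the maximum picks the latest of them. Two routes lead to unobserved time.

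- **Lost with a diary outstanding.** Loss to follow-up is declared after repeated missed visits and failed contact (Protocol 7.2: "where possible, 3 telephone calls and, if necessary, a certified letter"). The subject still holds the current diary. If the recorded discontinuation date is later than the last returned diary, the days between are counted as rescue-free. A subject lost before Visit 2 has returned no diary and, if a missing record is read as no use, is carried as a non-user.
- **Withdrawn early, then followed.** Protocol 8.2.1 withdraws some subjects at Visit 2 for laboratory abnormalities and follows them to resolution. Section 10.6 follows all adverse events. Section 8.4 adds: "The study site may contact a subject to follow up an AE post-study completion/withdrawal". If such a contact supplies the follow-up date, the subject stays at risk after the diary and tablets were handed back.

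At stake is the one formal between-arm test of rescue use in a trial that allows paracetamol in both arms. Tablet counts and yes/no use are otherwise only summarised.

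**Working it through.** **No figure to reproduce.** The documents give no rescue rate, event count, loss rate or power for this endpoint. What follows is illustrative, and the rates are assumptions.

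**Length of the unobserved time.** Take a subject lost after Visit 2, with diary data to Day 3.
- Discontinuation dated Day 8: 8 − 3 = 5 unobserved days.
- Follow-up contact at the end of the 28-day adverse event period (Protocol 10.3.1), last dose on Day 7: 7 + 28 = Day 35, and 35 − 3 = 32 days. Only those up to about Visit 4 can affect the estimates, because no rescue events are recorded later.

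**Effect on cumulative use.** Let F(t) be the true probability of rescue use by Day t, with a constant daily hazard, so F(t) = 1 − [1 − F(8)]^(t/8). A fraction d of an arm has rescue data only to Day L, and loss is unrelated to rescue use. If these subjects are held at risk through Day 8, nobody is censored earlier and Kaplan-Meier is the simple proportion with a recorded event:

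SAP estimate = (1 − d) × F(8) + d × F(L)

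Understatement = d × [F(8) − F(L)]

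For F(8) = 50%: F(2) = 1 − 0.5^0.25 = 0.159 and F(4) = 1 − 0.5^0.5 = 0.293. With d = 10%:
- L = 0: 0.9 × 0.5 = 45.0%
- L = 2: 0.45 + 0.1 × 0.159 = 46.6%
- L = 4: 0.45 + 0.1 × 0.293 = 47.9%

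| True use by Day 8 | Loss d | L = 0 | L = 2 | L = 4 | Understatement (points) |
|---|---|---|---|---|---|
| 30% | 5% | 28.5% | 28.9% | 29.3% | 0.7–1.5 |
| 30% | 10% | 27.0% | 27.9% | 28.6% | 1.4–3.0 |
| 50% | 5% | 47.5% | 48.3% | 49.0% | 1.0–2.5 |
| 50% | 10% | 45.0% | 46.6% | 47.9% | 2.1–5.0 |
| 60% | 5% | 57.0% | 58.0% | 58.8% | 1.2–3.0 |
| 60% | 10% | 54.0% | 56.0% | 57.7% | 2.3–6.0 |

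Censoring at Day L returns the true value in every row. The median moves little: at 60% use it is Day 7 with diary censoring and Day 7 or 8 under the SAP rule; at 30% neither rule reaches it. At 50% it sits on the boundary, so a median not reached there reflects the chosen rate.

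**Effect on the log-rank test.** The simulation used 150 per arm, no true difference, 2000 runs, last diary day 0, 2 or 4 with equal probability for lost subjects, and lost subjects kept at risk past Day 8 under the SAP rule. The Monte Carlo standard error near 5% is √(0.05 × 0.95 / 2000) = 0.5 points.

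| Loss by arm | True use | Type I error, SAP rule | Type I error, diary censoring |
|---|---|---|---|
| 10% / 10% | 30% | 5.6% | 5.3% |
| 10% / 10% | 50% | 4.9% | 4.5% |
| 5% / 15% | 30% | 6.8% | 4.5% |
| 5% / 15% | 50% | 8.9% | 5.5% |
| 5% / 20% | 30% | 9.5% | 4.7% |
| 5% / 20% | 50% | 14.2% | 5.2% |

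The last two rows are a stress case, not an expectation.

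**The case against.** The best defence is that few subjects are exposed. A withdrawn subject who attends the early-termination visit returns the diary then, so discontinuation and the end of observation coincide unless a later follow-up date is taken. This stands. So does the point about completers: a date after Visit 4 adds only a flat tail beyond the last event, with at most a small effect inside the ±1-day visit window.

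Two links are inferred. Protocol 7.1 requires a date to be recorded with the reason for discontinuation, but the documents do not say whether for a lost subject this is last contact or declared loss. If it is last contact, and no later follow-up date enters, much of the false time disappears. SAP 4.4.3 also lists a yes/no rescue field and does not say that missing means no. These limit the number affected, but nothing in the SAP excludes either problem, and the maximum can run past the discontinuation point that SAP 4.5.3 sets for withdrawn subjects.

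Tablet counts at Visits 2 to 4 can reveal use, but do not date it and also require attendance.

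A reader might infer that the rule could conceal paracetamol use that explains similar Day 5 pain. The documents do not support this. Subjects lost before Visit 3 have no Day 5 pain score and are listed for exclusion from the per-protocol set, on which the SAP runs its primary analysis without imputation. For subjects lost after Visit 3, the unseen use falls after the Day 5 measurement. A reader might also take the gap between 300 randomized and 240 evaluable as 20% loss. It is an allowance for all per-protocol exclusions, including eligibility, compliance and prohibited medication, and is not a loss rate.

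**Conclusion.** The point holds in limited form. The stated rule gives unobserved rescue-free time to subjects lost with a diary outstanding (if discontinuation is dated after the last returned diary) and to early withdrawals with a later follow-up date. The error always runs towards too little rescue use: about 1 to 5 points at 5–10% loss if true use is 50%, and about 1 to 6 points across assumed use of 30–60%. Between-arm bias needs unequal loss, and the documents give no reason to expect it in a one-week trial; with equal 10% loss the test keeps its level. The size rests on assumed rates, a constant hazard and loss unrelated to rescue use. The primary non-inferiority analysis and the sample size are not affected. It is still worth correcting, because the rule is wrong as written and the repair is simple.

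**What to change.** In SAP 4.4.3, before unblinding:

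1. Define the censoring date as the last calendar day covered by a returned diary or rescue-medication record, no later than discontinuation or Visit 4. Drop the follow-up date from the definition.
2. Treat subjects with no returned diary as having no rescue information: censor them at Day 1, ahead of any Day 1 event so that they add no time at risk, and report their number by arm. Do not count them as non-users, either here or in the yes/no summary.
3. Diary-based censoring is unbiased only if loss is unrelated to rescue use. Add a sensitivity analysis that counts withdrawal without a returned diary as an event.

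The cost is one definition, a small programming change and one extra analysis, with no new data. The downside is slightly fewer subjects at risk on later days.

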## 4.5 Analysis of Efficacy

#### 4.5.1 Primary Efficacy Endpoint

#### 4.5.1.1 Primary Efficacy Endpoint Definition

The primary efficacy endpoint is change from baseline in Pain On Movement (POM) on Day 5 of treatment as assessed by a 100 mm VAS scale.

#### 4.5.1.2 Statistical Hypothesis, Model, and Method of Analysis

The hypothesis of the study is stated below:

H0: The Diclofenac 2.32% DDEA Gel administered BID is inferior to Diclofenac1.16% DDEA gel administered QID.

 $\mu_T \text{-} \mu_S \geq \delta$ 

Where,  $\mu_S$  is the mean for a standard therapy (Diclofenac 1.16% DDEA Gel administered QID) and  $\mu$ T is the mean for test therapy (Diclofenac 2.32% DDEA Gel administered BID).  $\delta$  is the non-inferiority margin of 13 mm.

H1: Diclofenac 2.32% DDEA Gel administered BID is non-inferior to Diclofenac 1.16% DDEA gel administered QID.

 $\mu_T \text{ - } \mu_s < \delta$ 

 $\delta = 13 \text{mm}$ 

The primary efficacy analysis will be performed on PP population without imputation of missing data. The primary endpoint (Change from baseline in POM ) will be analysed using

GlaxoSmithKline Consumer Healthcare Confidential

Page **19** of **36** 

211206

Statistical Reporting and Analysis plan Draft V2.0 20JAN2021

Analysis of Covariance (ANCOVA) model with treatment and center as factors and baseline POM as covariate.

Diclofenac 2.32% DDEA Gel administered BID will be declared non-inferior to Diclofenac 1.16% DDEA gel administered QID if the upper limit of the two-sided 95% confidence interval of the difference between their mean changes from baseline VAS POM responses is less than the established margin of 13 mm.

Refer sample SAS code in APPENDIX 4.

Assumptions of normality and homogeneity of variances in the ANCOVA model will be evaluated after study un-blinding. If violations are observed then the following will be performed as a post-hoc sensitivity analysis and results will be compared with primary analysis results:

- 1. Suitable data transformations will be tried to achieve the assumptions.
- 2. If suitable transformations cannot be found, then the non-parametric Van Elteren tests will be performed using center as strata. Two sided 95% CI and p value will be presented.

POM by 100 mm VAS analogue scale (CRF page: Pain on Movement ; variable VASSCRL)will be summarized over time (**PPD**) using mITT population. Also POM by 100 mmVAS analogue scale will be summerarized over time by center using mITT population (**PPD**). Above tables (**PPD**) will be repeated for the PP population. POM by 100 mm VAS analogue scale for COVID 19 patients if any will be summarized in **PPD** using mITT population.

Statistical analysis for the primary endpoint will be dispayed in the tables (**PPD**) with mITT and PP population respectively.

#### 4.5.1.3 Supportive Analyses

To assess the treatment-by-center interaction an additional analysis will be performed for the primary endpoint on mITT population as following, where change from baseline on POM will be analysed using ANCOVA model with treatment, center as fixed factor, baseline POM as covariate and treatment-by-center as interaction (PPD)
 If there is evidence of an significant interaction (p<0.05) effect, then the primary endpoint outcome will also be summarized by center for further investigation and assessment.

GlaxoSmithKline Consumer Healthcare Confidential

Page 20 of 36

Reference SAS code is given in APPENDIX 4:

- 2. Sensitivity analysis will be perfomed on POM for compliance category -good. For good category greater than or equal to 80% compliance will be considered for both in application and amount of gel used for this sensitivity analysis. The sensitivity analysis for the primary endpoint will be dispayed in the tables (**PPD**).
- 3. The primary efficacy endpoint will be analyzed using ANCOVA model on ITT population using imputed data.
- 4. The Change from baseline on POM will be analyzed using Mixed Model Repeated Measure (MMRM) with multiple imputation (day 3,5,8) model with treatment, center as fixed factor, baseline POM as covariate and visit as repeated measure; using ITT population.
- 5. Same as above mentioned point 3 without imputed data, ie, observed data.
- 6. Same as above point 3 using PP population.
- 7. Same as above point 4 using PP population.

Early discontinued subjects data due to any reason- will be analyzed in this section using imputation.

#### 4.5.2 Secondary Efficacy Variables

The secondary efficacy analyses will be performed and also be listed on mITT and PP population.

- Change from baseline of POM (CRF page: Pain on Movement; VAS score will be obtained from VASSCRL) on VAS on days 3 and 8 respectively (PPD).
- Tenderness measured by pressure algometry on days 3, 5 and 8 which will be analysed using change from baseline and difference between the measurement in injured area (CRF page: Tenderness; measurement for study ankle : QS\_INJA) and contralateral area (CRF page: Tenderness; measurement for study ankle : QS\_CLTA) (PPD)...
- Change from baseline Ankle Joint Function (Karlsson Scoring Scale; CRF page: Ankle Joint Function: Variable : Total Score KSSTS) on days 3, 5 and 8 (PPD)...
- Circumference measurement of swelling on days 3, 5 and 8 which will be analysed using change from baseline in circumference of affected ankle and comparison to non-affected ankle by Figure of Eight method (CRF Page:Ankle swelling; Variables: FOEMINSC and FOEMCASC respectively.) (PPD)...

GlaxoSmithKline Consumer Healthcare Confidential

Page 21 of 36

211206

Statistical Reporting and Analysis plan Draft V2.0 20JAN2021

- Pain Intensity and Pain Relief (CRF Page: Subject Diary(Day 1/5); variables will used to calculate the Pain Intensity and Pain Relief are DPI and DPR respectively for each timepoint (DSTMPT))
- Pain Intensity (**PPD**)..
  - Pain intensity will be analysed based on the Sum of Pain Intensity Difference (SPID). SPID is defined as from 0 -24 hours post first dose corresponding to day 1 and from 0-24 hours post first dose corresponding to day 5.
  - SPIDt=>PIDt(timet-timet-1)(h), where, PIDt=pain intensity score (DPI from CRF page corresponding to day); timet=time in hours post first dose
  - Pain Relief (**PPD**)...:
    - Pain relief will be analysed based on the Total Pain Relief (TOTPAR). TOTPAR is defined as from 0-24 hours post first dose corresponding to day 1 and from 0-24 hours post first dose corresponding to day 5.
    - TOTPAR=∑Rt(timet-timet-1), whert e Rt=pain relief score (DPR from CRF page corresponding to day)

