12 STATISTICAL CONSIDERATIONS AND DATA ANALYSES

12.1 Sample Size Determination

Approximately 300 subjects will be randomized to ensure at least 240 evaluable subjects complete the study for the PP analysis population. A maximum of 40 randomized subjects per center will be allowed.

Approximately 120 subjects per treatment arm has been determined to provide 80% power to demonstrate non-inferiority of DDEA 2.32% gel b.i.d with DDEA 1.16% gel q.i.d. by comparing the two-sided 95% CI of the difference in mean change from baseline of VAS POM score between the two products with the non-inferiority margin of 13 mm. This assumes a treatment standard deviation of 22mm and allows for a possible small true treatment difference of 5mm in favor of DDEA 1.16%.

The margin of 13 mm (on a 100 mm VAS scale) was chosen as the literature reported minimally important clinical difference for an acute musculoskeletal injury (Todd et al 1995), with treatment differences smaller than 13mm considered as not clinically important. The standard deviation was obtained from a previous placebo-controlled ankle sprain study VOPO-P-307 with DDEA 2.32% gel.

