12.2.6 Secondary Analysis(es)

Secondary outcome measures (endpoints) include:

- Change from baseline of POM on VAS on Days 3 and 8 respectively
- Tenderness measured by pressure algometry on Days 3, 5 and 8 (change from baseline and difference between the measurement in injured area and contralateral area)
- Change from baseline Ankle Joint Function (Karlsson Scoring Scale) on Days 3, 5 and 8
- Circumference measurement of swelling (change from baseline in circumference of affected ankle and comparison to non- affected ankle by Figure of Eight method on Days 3, 5 and 8)
- Pain Intensity and Pain Relief
 - Sum of Pain Intensity Difference (SPID) From hours 0 24 post first dose (corresponding to Day 1) and from hours 96 120 post first dose (corresponding to Day 5)
 - Total Pain Relief (TOTPAR) From hours 0 24 post first dose (corresponding to Day 1) and from hours 96 120 post first dose (corresponding to Day 5)

TOTPAR and SPID will be calculated as weighted sums of the Pain Relief Score and Pain Intensity Difference at each timepoint respectively:

 $TOTPAR = \Sigma R_t^x (time_t - time_{t-1})$

Where R_t = the pain relief score at time t and time t = time in hours post first dose

 $SPID_t = \Sigma PID_t (time_t - time_{t-1})(h)$

Where PI is pain intensity

- Use of rescue medication, for ankle sprain and overall
 - Total number of tablets used
 - Total number of days on which rescue medication was used

Figures will show the time course of outcomes by treatment group for key quantitative outcomes.

For POM, Karlsson score, tenderness, swelling and diary assessments (SPID and TOTPAR), an ANCOVA model including treatment group and center as main effects, and the baseline value as covariate (those outcomes for which there is a baseline) will be used for analysis, with the treatment difference and 95% confidence interval (two-sided) presented for each assessment.

Use of rescue medication (number of tablets and days used) will be compared between treatments using the CHM method (modridit scores) stratified by center, with the median treatment differences and 95% confidence intervals (2-sided) presented using Hodges-Lehmann estimation.

These secondary endpoints will be analyzed using the per protocol and mITT populations.

GlaxoSmithKline Consumer Healthcare Confidential Template Version Effective: 18-May-18 (CCR #11475) Page **54** of **64**

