#### 4.5.3 Handling of Missing Values/Censoring/Discontinuations

As a part of missing data analysis a Multiple Imputation (MI) simulation method for imputing missing data will be conducted on ANCOVA analysis for the primary efficacy endpoints on the ITT population. This will help to assess the impact of missing data on the primary analysis.

Subjects who withdraw from the study prematurely will also be included in the statistical analyses up to the point of discontinuation.

The SAS procedure MI will be used and the details of MI procedure will be stated in the dataset specification document. If the data is monotone missing, an imputation model with regression baseline parameters will be applied, otherwise Markov Chain Monte Carlo(MCMC) will be applied. All variables included in the analysis model which are used in the primary model will be used for imputation andvalues at day 3 for the primary endpoint (For Day 5) will be included in the imputation model. To reduce the sampling variability from the imputation process, 50 datasets will be generated.

In the estimation step, separate analysis will be performed using the model mentioned for the primary endpoint statistical analysis Section 4.5.1.2.

After the completion of the estimation step SAS procedure MIANALYZE will be used to pool the estimates.

Refer APPENDIX 4 for sample SAS codes.

GlaxoSmithKline Consumer Healthcare Confidential

Page 22 of 36

No imputation is planned for missing diary card pain intensity and relief assessments.

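### SPID and TOTPAR take diary scores after permitted paracetamol as recorded and leave the collected pre-rescue scores unused, which may attenuate the between-arm difference in these secondary endpoints

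*SAP*

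**What the plan says.** - **Rescue.** Paracetamol 500 mg is available throughout, one tablet at a time, at least 4 h apart, up to four a day (Protocol 6.10). Protocol 4.1 bars it for 6 h before each visit and for 12 h before Visit 3.
- **Diary.** Pain intensity (0 to 3) and pain relief (0 to 4) are scored every 2 h from the first dose on Day 1 until bedtime, and again from the first dose on Day 5 (Protocol 6.8 and 9.2.5).
- **Formulas.** Protocol 12.2.6: "TOTPAR and SPID will be calculated as weighted sums of the Pain Relief Score and Pain Intensity Difference at each timepoint respectively". SAP 4.5.2 and 4.6.1 take the inputs from the Day 1/5 diary page: "variables will used to calculate the Pain Intensity and Pain Relief are DPI and DPR respectively for each timepoint (DSTMPT"). Neither document has a rescue term.
- **Pre-rescue scores.** At each rescue dose the diary must also capture "Pain intensity and pain relief immediately prior to each dose of rescue medication" (Protocol 6.8). SAP 4.4.3 holds this as "Pain intensity (RMPI) and pain relief (RMPR) before taking rescue medication", on a separate CRF page, to be summarized and listed only.
- **Missing scores.** SAP 4.5.3: "No imputation is planned for missing diary card pain intensity and relief assessments". A score taken after rescue is not missing, so this sentence does not cover it.

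**The concern.** A scheduled score taken while paracetamol is working reflects gel plus paracetamol, and it enters SPID and TOTPAR with full weight. If subjects who get less from their gel take more tablets, their later scores improve and the arms move closer together. In a trial meant to show that nothing clinically important is lost, that is the flattering direction.

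The plan already collects the value needed to examine this and does not use it. The omission matters more because SAP Section 5 replaces the protocol's between-arm comparison of tablets and days with time to first rescue use. That measure is counted in whole days (SAP 4.4.3) and cannot show repeat dosing.

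At stake is the reading of two supportive endpoints, not the trial's success criterion.

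**Working it through.** **The plan's own figure.** The only stated design figure concerns pain on movement (POM): "Approximately 120 subjects per treatment arm has been determined to provide 80% power", "comparing the two-sided 95% CI of the difference in mean change from baseline of VAS POM score" "with the non-inferiority margin of 13 mm". With SD 22 mm and an assumed true difference of 5 mm:

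n per arm = 2 × 22² × (1.960 + 0.842)² / (13 − 5)² = 118.7, rounded up to 119.

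At 120 per arm the power is 80.4%, and 240 / 0.80 = 300 randomized. The figure reproduces, and this point does not bear on it. No margin, SD or rescue rate is given for SPID or TOTPAR, so everything below is illustration on assumed inputs.

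**Which diary hours are exposed.**
- Day 1: all hours after the first dose. With the 15:00 first dose used as an example in Protocol 6.2 and bedtime at 21:00 to 23:00 (assumed), that is 6 to 8 h.
- Day 5: with the same start, Visit 3 at 96 ± 4 h falls between 11:00 and 19:00. If the subject rises at 07:00 (assumed), 4 to 12 h of Day 5 diary precede the visit, all inside the 12 h ban. Only the hours after the visit are exposed.
- This uses the wording of Protocol 4.1. Protocol 6.8 and 6.10 do not say that the 12 h lie before Visit 3, and SAP 4.4.3 counts them from Day 5. These passages should be reconciled, since they set how much of Day 5 is exposed.

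**Algebra for SPID.** SPID units masked = excess tablets per subject in the weaker arm × intensity points removed per tablet × hours of effect. Take 4 h per tablet and 14 h of diary:
- A true deficit of 0.2 points is 0.2 × 14 = 2.8 units.
- Hiding all of it needs 2.8 / (1 × 4) = 0.7 excess tablets per subject at 1 point per tablet, or 2.8 / (0.5 × 4) = 1.4 at half a point.
- Over deficits of 0.1 to 0.3 points and 10 to 14 h, the need runs from (0.1 × 10) / (1 × 4) = 0.25 to (0.3 × 14) / (0.5 × 4) = 2.1.

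**Simulation for SPID.** Assumed: 14 h of two-hourly scores; baseline intensity 2 or 3 with equal probability; a latent deficit of 0.3 points; a tablet possible when recorded intensity is 2 or more, at least 4 h apart, at most four; 1 point removed for 4 h. Both arms have the same chance of taking a tablet at a given pain level, so the excess arises only from worse pain.

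| Chance of rescue | Tablets per subject, better / weaker arm | SPID difference as recorded | Shrinkage | Pre-rescue score carried 4 h |
|---|---|---|---|---|
| 0 | 0 / 0 | 3.67 | none | 3.67 |
| 0.25 | 0.89 / 1.04 | 3.21 | 13% | 3.63 |
| 0.50 | 1.46 / 1.71 | 2.87 | 22% | 3.58 |
| 0.75 | 1.86 / 2.17 | 2.65 | 28% | 3.55 |

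Shrinkage is 1 − (as recorded / 3.67). The excess tablets are 0.15, 0.25 and 0.31 per subject. The algebra would predict 0.60, 1.00 and 1.24 units masked (excess × 1 × 4). The simulation lost 0.46, 0.80 and 1.02, partly because a late tablet's effect runs past the last score.

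Two limits: the simulation carried the pre-rescue score in every case, not only when it was worse, and TOTPAR was not simulated.

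**The case against.** The case for leaving the plan alone has real content.

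- **As-recorded scoring is a legitimate choice.** It compares gel plus permitted rescue, under identical rules in both arms. This stands, although neither document states that it is the intended question. It is why the as-recorded version should be kept.
- **Little decision weight.** Success rests on Day 5 POM alone (Protocol Section 3). SPID and TOTPAR get a difference and a 95% CI, with no non-inferiority test. This stands.
- **Rescue is reported separately.** Tablets, reasons, pre-rescue scores and time to first use are all shown, so a marked imbalance would be partly visible. This stands in part: with the comparison of tablets and days dropped, repeat use appears only descriptively.
- **The window is debatable.** Four hours is a minimum re-dosing interval, not a stated duration of effect. Replacing a score only when the pre-rescue value is worse moves scores one way, and it also affects tablets taken for headache or fever. These are fair reasons to treat the result as a sensitivity analysis.

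A reader might also infer more than the documents support:
- **That a weaker gel would look equal.** Full masking appears only in the algebra, at an excess of 0.25 to 2.1 tablets per subject. In the simulation the difference shrank and did not vanish, and with equal rescue use the bias is small.
- **That the effect is 33% or 100%.** One rescue user with a constant intensity difference of 1 over 12 h moves from 12 to 16 units with one tablet (12 + 1 × 4), or to 24 with tablets every 4 h (12 + 1 × 12). Those are assumed changes within one subject, not differences between arms.
- **That no other endpoint captures pain over the week.** The Karlsson scale has a 20-point pain category at all four visits (Protocol 9.2.4), and the diary is also scored before each gel application on the other days.

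**Conclusion.** The gap is confirmed in a limited form. Scheduled scores after permitted paracetamol enter SPID and TOTPAR unchanged on Day 1 and on Day 5 after Visit 3. The pre-rescue scores exist and are unused, and no rule addresses the matter.

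The consequence is conditional: the between-arm difference may be attenuated if the arm with less gel benefit uses more rescue. The 13% to 28% shrinkage rests wholly on assumed pain courses, rescue behavior and a 1-point, 4 h paracetamol effect, over a 14 h diary that is longer than the Day 1 period in the protocol's 15:00 example. It is not an estimate for this trial. The primary POM conclusion, its sample size and its power are unaffected.

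**What to change.** Before unblinding, add to SAP 4.5.2 and 4.6.1 a sensitivity SPID and TOTPAR for Day 1 and Day 5:

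1. For each scheduled score within a pre-specified window after any rescue dose, substitute RMPI for intensity or RMPR for relief when the pre-rescue value is worse (higher intensity, lower relief).
2. Treat the window as an analysis convention that the sponsor justifies. Four hours, taken from the protocol's minimum re-dosing interval, is one example.
3. Run the same ANCOVA on mITT and PP, and report it beside the as-recorded version.

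The same edit can correct the definition of PID, which the SAP equates with the intensity score itself instead of a difference from baseline.

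The cost is one repeated derivation and one extra table from data already on the CRF. The downside is that the second version answers a slightly different question, namely the effect without rescue benefit. The SAP is still labelled a draft, and its Section 2.2 puts finalization before unblinding, so the rule can be set blind. Rescue rules do not change.
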